Appendix A. ASAS-NSAID Intake Score for Axial Spondyloarthritis

ASAS-NSAID Intake Score for Axial Spondyloarthritis: The amount of NSAID intake could be considered as a clinically relevant outcome measure in ankylosing spondylitis (AS)/axial spondyloarthritis.

To be able to calculate the ASAS-NSAID Intake Score, the following information is required:

(1) the type of NSAID/Cox2 inhibitor: each NSAID has a corresponding weight factor. The weight is determined by the maximum dose of each NSAID to achieve a score of 100. The goal is to analyze/report the data in terms of NSAID equivalent dose in mg/day on a 0 - 100 scale. The 150 mg equivalent diclofenac is set to 100. For instance, 150 mg Diclofenac is equivalent to 1000 mg Naproxen, so the weight for Diclofenac is 100/150, and, the weight for Naproxen is 100/1000. For other NSAIDs/COX2 inhibitors not described in table the weight factor will be determined based on medical review using the local label as a guide.

NSAID	Weights
Diclofenac	100/150
Naproxen	100/1000
Aceclofenac	100/200
Celecoxib	100/400
Etodolac	100/600
Etoricoxib	100/90
Flurbiprofen	100/200
Ibuprofen	100/2400
Indometacin	100/150
Ketoprofen	100/200
Meloxicam	100/15
Nimesulide	100/200
Phenylbutazone	100/400
Piroxicam	100/20
Tenoxicam	100/20

(2) the dose: mg per intake

(3) the frequency: days of intake per week (the times of intake daily)

Frequency Description	Numeric Frequency
QD	1
BID	2
TID	3
QID	4
1 time per week	1/7
2 times per week	2/7
3 times per week	3/7
4 times per week	4/7
5 times per week	5/7
6 times per week	6/7

(4) days of intake during the period of interest: can be calculated by NSAID end date - start date + 1.

(5) days stayed on study in the clinical trial: is defined as the total number of days in the study = last visit date – baseline date + 1.

Then, two scores can be calculated:

1. **Equivalent NSAID score** = weights * dose(mg) * (numeric frequency),

where weights can be obtained from the weight table (above and Dougados et al. Ann Rheum Dis 2011; 70:249–251), and dose is the number of mg per intake, numeric frequency is the number of intakes per day. The equivalent NSAID score is a scoring system to refer to a scale in which 0 equals no intake, and 100 equals 150 mg diclofenac, or 1000 mg naproxen, or 200 mg aceclofenac, or 400 mg celecoxib etc per daily dose.

2. ASAS-NSAID Intake Score =

(Equivalent NSAID score) * (days of intake during period of interest)/(days stayed on study in the clinical trial)

Appendix B. EAER and Normal Approximation Based 95% Confidence Interval

Assume the occurrence of TEAE of special interest follows a Poisson distribution and let λ denote the rate of occurrence of TEAE under the total exposure time for a treatment group. Let n be the number of AEs reported in Any Upadacitinib 15 mg QD group. Let T be the total number of days exposed to study drug summed across all treated subjects in Any upadacitinib 15 mg QD group. Under the assumption that n follow Poisson distribution with parameters λT , the $\hat{\lambda} = n/T$.

Using normal approximation, the 95% confidence interval can be calculated by (Liu GF, et al. 2006.):

$$\hat{\lambda} \pm Z_{\alpha/2} \hat{\sigma}$$

Where $\hat{\sigma} = \sqrt{\frac{n}{T^2}}$

Appendix C. Analysis of Categorical Endpoints

Binary endpoints

The point estimate of the response rate for each treatment group is calculated as $\hat{p} = \frac{k}{N}$ where k denotes the number of responders in the treatment group and N denotes the total number of subjects in the treatment group. The corresponding 95% CI is based on normal approximation, that is $\hat{p} \pm Z_{0.975} \sqrt{\frac{1}{N} \hat{p}(1 - \hat{p})}$, where $Z_{0.975}$ denotes the 97.5% quantile of the standard normal distribution. This is implemented by obtaining the Wald asymptotic confidence limits using the SAS procedure PROC FREQ with the BINOMIAL option. The SAS code example is as follows:

```
proc freq data=TESTData1;
  by TRTP;
  tables RESP / binomial(level="1") alpha=0.05;
  weight COUNT/zero;
  output out=CI(keep= L_BIN U_BIN) binomial;
run;
```

Note: The input dataset is cell count data, with variable RESP denoting response status ("1" as responder and "0" as non-responder) and variable COUNT denoting the number of subjects with the corresponding response status.

The treatment difference is calculated as $\hat{p}_1 - \hat{p}_2$, and the corresponding 95% CI for the treatment difference is based on normal approximation, that is $\hat{p}_1 - \hat{p}_2 \pm Z_{0.975} \sqrt{\frac{1}{N_1} \hat{p}_1(1 - \hat{p}_1) + \frac{1}{N_2} \hat{p}_2(1 - \hat{p}_2)}$. This is implemented by obtaining the Wald asymptotic confidence limits using the SAS procedure PROC FREQ with the RISKDIFF option. The SAS code example is as follows:

```
proc freq data=TESTData1;
  tables TRTP*RESP / riskdiff alpha=0.05;
  weight COUNT/zeros;
  where TRTP in ('PLACEBO', 'UPA 15MG');
  output out=diff(keep= _RDIF1_ L_RDIF1 U_RDIF1) riskdiff1;
run;
```

Note: The input dataset is cell count data, with variable RESP denoting response status ("1" as responder and "0" as non-responder) and variable COUNT denoting the number of subjects with the corresponding response status. TRTP denotes the treatment group.

The p-value for the treatment comparison is based on the Cochran-Mantel-Haenszel (CMH) test adjusting for stratification factor. This is implemented using the SAS procedure PROC FREQ with the CMH option. The p-value from the "general association statistic" is used. The SAS code example is as follows:

```
proc freq data=TESTData3;  
  tables STRATA*TRTP*RESP_VALUE / cmh;  
run;
```

Note: The input dataset is subject-level data, with variable RESP_VALUE denoting the subject's response status ("1" as responder and "0" as non-responder). TRTP denotes the treatment group and STRATA denotes the strata for a given subject.

Categorical endpoints with more than 2 categories

The extended Cochran-Mantel-Haenszel test is used to assess the association among a set of q -by- r tables, where r is the number of levels in the ordinal categorical endpoints. For the case of insomnia severity index (ISI) which has $r = 4$ levels, the extended CMH test is stratified by hsCRP level that has $q = 2$ strata. The analysis is to assess the association between treatment and ISI, adjusting for the hsCRP level.

The following PROC FORMAT declaration is to ensure that the ISI categories are properly ordered in the analysis.

```
/*PROC FORMAT to ensure that the ISI categories are correctly ordered*/  
proc format;  
  value ISICat  
  1 = "No clinically significant insomnia"  
  2 = "Subthreshold insomnia"  
  3 = "Clinical insomnia (moderate severity)"  
  4 = "Clinical insomnia (severe)";  
run;
```

Denote n_{hij} the number of subjects who are in hsCRP stratum h ($h = 1, \dots, q$), treatment group i ($i = 1, 2$) and have ISI category j ($j = 1, \dots, r$). Also suppose $\{a_{h1}, \dots, a_{hr}\}$ is a set of scores associated with each level of the response variable in stratum h . In this

analysis, we use the SAS default "integer scores" such that $\{a_{h1}, \dots, a_{hr}\} = \{1, \dots, r\}$ for $h = 1, \dots, q$.

The sum of strata scores for treatment $i = 1$ is

$$f_{+1+} = \sum_{h=1}^q \sum_{j=1}^r a_{hj} n_{h1j}$$

Under the null hypothesis of no association, f_{+1+} has the expected value and variance

$$E\{f_{+1+}|H_0\} = \sum_{h=1}^q n_{h1+} \mu_h = \mu_*,$$

$$V\{f_{+1+}|H_0\} = \sum_{h=1}^q \frac{n_{h1+}(n_h - n_{h1+})}{n_h - 1} v_h = v_*,$$

where $\mu_h = \sum_{j=1}^r (a_{hj} n_{h+j}/n_h)$ is the finite subpopulation mean and $v_h = \sum_{j=1}^r (a_{hj} - \mu_h)^2 (n_{h+j}/n_h)$ is the variance of scores for stratum h .

The extended CMH test statistic is

$$Q_{SMH} = \frac{(f_{+1+} - \mu_*)^2}{v_*}$$

which has an approximate chi-square distribution with one degree of freedom. The following PROC FREQ implements the test for ISI and the test statistics Q_{SMH} corresponds to "Row mean scores differ" in the output.

```
/*ORDER=FORMATTED is critical*/
proc freq data=ISI order=formatted;
table hsCRP*Treatment*ISICat / cmh nocum nocol nopercnt;
run;
```

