4.2 Overall Study Design and Plan

This is a Phase 2/3, multicenter study that includes two periods. Period 1 is the 14-week randomized, double-blind, parallel-group, placebo-controlled period designed to compare the safety and efficacy of Upadacitinib 15 mg QD versus placebo for the treatment of signs and symptoms of subjects with active AS who have had an inadequate response to at least two NSAIDs over an at least 4-week period in total at maximum recommended or tolerated doses or intolerance to or a contraindication for NSAIDs as defined by the Investigator, and who are bDMARDs-naïve. Period 2 is an open label long-term extension to evaluate the long-term safety, tolerability, and efficacy of Upadacitinib 15 mg QD in subjects with AS who have completed Period 1.

The study is designed to enroll approximately 170 subjects at approximately 110 study centers worldwide to meet scientific and regulatory objectives without enrolling an undue number of subjects in alignment with ethical considerations.

The study duration includes a 35-day screening period; a 14-week randomized, double-blind, placebo-controlled treatment period (Period 1); a 90-week open label extension period (Period 2); and a 30-day follow-up visit. After Week 104, subjects in France, Germany, Belgium, Finland, and Netherlands will be evaluated for safety and tolerability of upadacitinib every 12 weeks until the end of the study.

X-rays of the pelvis will be performed within the 35-day screening period to evaluate the SI joints to confirm the fulfillment of the modified New York Criteria for AS. X-rays of the spine will also be performed within the 35-day screening period to assess for total spinal ankylosis; subjects with total spinal ankylosis are not eligible for this study. The x-rays of the spine and pelvis will not be required during the Screening Period if the subject had a previous anteroposterior (AP) pelvis x-ray and lateral spine x-rays within

90 days of the Screening Period, provided that the x-rays are confirmed to be adequate for the required evaluations and are deemed acceptable by the central imaging vendor.

Subjects who meet eligibility criteria will be randomized in a 1:1 ratio to one of two treatment groups:

- Group 1: Upadacitinib 15 mg QD, N = 85 (Day 1 to Week 14) → Upadacitinib 15 mg QD (Week 14 and thereafter)
- Group 2: Placebo, N = 85 (Day 1 to Week 14) → Upadacitinib 15 mg QD (Week 14 and thereafter)

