9.1.2 Handling for Missing Data and Intercurrent Event

Non-Responder Imputation (NRI) Approach

The NRI approach will handle data for binary variables as follows.

- Subjects who prematurely discontinue from study drug will be considered as non-responders for all subsequent visits after discontinuation.

- In addition, any subject with any missing value for binary variables at a specific visit will be treated as non-responder for that visit.

The NRI data handling will be used for the primary estimand (refer to Section 9.2.1) for binary variables.

As Observed (AO)

The AO data handling will not impute values for missing evaluations, and thus a subject who does not have an evaluation on a scheduled visit will be excluded from the AO analysis for that visit. Regardless of premature discontinuation of study drug, all observed data will be used in the analysis. The AO data handling will be used to facilitate the supplementary analysis for both binary and continuous variables (refer to Section 9.2.2 and Section 9.2.3 where the corresponding supplementary estimand for the primary and ranked secondary endpoints is described respectively).

Mixed Effect Model Repeat Measurement (MMRM)

The repeated measure analysis will be conducted using mixed model including observed data at all visits. For the MMRM analysis, data collected after premature discontinuation of study drug will be excluded. The mixed model includes the categorical fixed effects of treatment, visit and treatment-by-visit interaction, main stratification factors at randomization and the continuous fixed covariates of baseline measurement. An unstructured variance covariance matrix will be used. The parameter estimations are based on the assumption of data being missing at random and using the method of restricted maximum likelihood (REML). MMRM will be used for the primary estimand of continuous variables (refer to Section 9.2.3).

Longitudinal Analysis for Long-Term Efficacy: MMRM and Generalized Linear Mixed Model (GLMM)

The repeated measure analysis will be conducted using mixed model including AO measurements at all visits. MMRM will be used for continuous endpoints and GLMM will be used for binary endpoints. The mixed models will include the categorical fixed

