9.2.3 Key Secondary Efficacy Analyses

The key multiplicity adjusted secondary efficacy endpoints at Week 14 are:

1. Change from Baseline in Ankylosing Spondylitis Disease Activity Score (ASDAS(CRP));
2. Change from Baseline in MRI Spondyloarthritis Research Consortium of Canada (SPARCC) score (Spine);

3. Proportion of subjects with BASDAI 50 response (defined as 50% improvement in the Bath AS Disease Activity Index);
4. Change from Baseline in AS QoL;
5. Proportion of subjects with ASAS partial remission (PR) (defined as an absolute score of ≤ 2 units for each of the four domains identified in ASAS 40);
6. Change from Baseline in BASFI;
7. Change from Baseline in BASMI_{lin};
8. Change from Baseline in MASES (for subjects with baseline enthesitis);
9. Change from Baseline in WPAI (the overall work impairment due to SpA);
10. Change from Baseline in ASAS HI.

Additional key secondary endpoints are:

- ASAS 20 response at Week 14.
- Change from Baseline in MRI SPARCC score (SI joints) at Week 14.

For binary endpoints, frequencies and percentages will be reported for each randomized treatment group. The primary estimand is the same as that for the primary efficacy endpoint as defined in Section 9.2.1, except for the definition of the efficacy measurement. NRI data handling will be used to analyze the primary estimand.

Supplementary analysis using AO data handling will also be conducted. The corresponding supplementary estimand is the same as defined in Section 9.2.2 except for the definition of the efficacy measurement. To explore various missing data assumptions including missing not at random (MNAR), tipping point analysis will also be conducted for ASAS 20 at Week 14 and details of the analysis are outlined in Appendix E.

Point estimate and 95% CI using normal approximation will be provided for the response rate for each randomized treatment group. Treatment comparisons will be made between

upadacitinib and the placebo group using the Cochran-Mantel-Haenszel. The CMH test adjusts for the main stratification factor of hsCRP level (\leq ULN vs. $>$ ULN). Point estimate, 95% CI using normal approximation and the p-value for the treatment difference will be presented.

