9.3 Long-Term Efficacy Analysis

Assessments to evaluate long-term efficacy will be analyzed for all efficacy measurements at scheduled visits.

Descriptive statistics will be provided for each randomized treatment group sequence as defined in Section 9.1.1. These include the number of observations, mean, standard deviation, 95% CI, for continuous endpoints; and frequencies and percentages with 95% CI using normal approximation for binary endpoints. Plot for each randomized treatment group sequence over time will be provided for primary and ranked secondary endpoints. These efficacy analyses will be based on As Observed (AO) analysis. In addition, longitudinal analysis will be performed using MMRM or GLMM as described in Section 9.1.2 for all endpoints except for radiographic endpoints. Point estimates and 95% CI from the model will be provided for each treatment group sequence.

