9.4.4 ASAS20, ASAS40, ASAS 5/6, and ASAS Partial Remission

Parameters used for the ASAS responses:

- Patient's Global Assessment – Represented by the PTGA-disease activity (NRS score 0 - 10)
- Pain – Represented by the patient's assessment of total back pain (NRS score 0 - 10)
- Function – Represented by the BASFI (NRS score 0 - 10)
- Inflammation – Represented by the mean of the 2 morning stiffness-related BASDAI (mean of items 5 and 6 of the BASDAI NRS score 0 – 10)

ASAS20 Response

Improvement of $\geq 20\%$ and absolute improvement of ≥ 1 unit (on a scale of 0 to 10) from Baseline in ≥ 3 of the above 4 domains, with no deterioration in the remaining domain (defined as a worsening of $\geq 20\%$ and a net worsening of ≥ 1 unit).

ASAS40 Response

Improvement of $\geq 40\%$ and absolute improvement of ≥ 2 units (on a scale of 0 to 10) from Baseline in ≥ 3 of the 4 domains above with no deterioration (defined as a net worsening of > 0 units) in the potential remaining domain.

ASAS Partial Remission

Absolute score of ≤ 2 units for each of the 4 domains identified above.

ASAS 5/6 Response

Improvement of $\geq 20\%$ from Baseline in 5 out of the following 6 domains: BASFI, patient's assessment of total back pain, PTGA-disease activity, inflammation (mean of Items 5 and 6 of the BASDAI), lateral lumbar flexion from BASMI, and hs-CRP.

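### SAP Appendix C gives each arm's response rate a Wald interval with no low-count alternative, so descriptive limits for rare responses such as placebo ASAS partial remission can be degenerate or under-cover

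*SAP*

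**What the plan says.** SAP Appendix C (Binary endpoints) defines the single-arm estimate as responders over subjects, k/N. Of its interval it says "The corresponding 95% CI is based on normal approximation". The limits are p ± 1.96·√(p(1−p)/N), and the software is fixed too: "This is implemented by obtaining the Wald asymptotic confidence limits using the SAS procedure PROC FREQ with the BINOMIAL option". There is no truncation at zero and no rule for zero or small counts.

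Section 9.2.3 applies this to the binary key secondary endpoints: "Point estimate and 95% CI using normal approximation will be provided for the response rate for each randomized treatment group". ASAS partial remission is fifth on that list, and Section 9.4.4 defines it as "Absolute score of ≤ 2 units for each of the 4 domains identified above". Section 9.2.1 uses the same type of interval for the primary endpoint. Section 9.2.4 uses it for exploratory binary endpoints, including ASDAS inactive disease (score below 1.3) and ASAS 40 at other visits. Section 9.3 uses it for long-term data: "frequencies and percentages with 95% CI using normal approximation for binary endpoints".

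P-values come separately from the CMH test (Appendix C).

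**The concern.** The Wald interval estimates its standard error from the observed proportion, so it shrinks as that proportion approaches zero and vanishes when there are no responders. A table entry of 0% with limits 0% and 0% claims a certainty that 85 subjects cannot supply. An entry of 1.2% with limits −1.1% and 3.5% includes impossible values and is too low at the upper end.

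Several features of the plan make small counts foreseeable in the placebo arm:

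- Partial remission needs all four domains at 2 or below, in subjects who enter with BASDAI and total back pain of at least 4 (Protocol Section 5.2.1).
- Protocol Section 3.0 puts remission at only about 15% to 20% with available treatment.
- Under non-responder imputation (SAP Section 9.1.2), "any subject with any missing value for binary variables at a specific visit will be treated as non-responder for that visit", which keeps the full arm in the denominator and can only lower the observed rate.

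At stake is the honesty of the reported uncertainty around a low arm-level rate. No test decision is at stake.

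**Working it through.** **Inputs.** N = 85 per arm (SAP Section 4.2). Single-arm formula from Appendix C, z = 1.96. ASAS 40 planning rates of 20% on placebo and 20% + 26% = 46% on upadacitinib (Protocol Section 8.2, SAP Section 4.3). The true placebo rate for the rarer endpoints is not in the documents, so it is varied from 0.5% to 20% as an assumption.

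**The plan's own figure.** Two-sided 0.05, 20% against 46%: power is 95.7% with 85 per arm and 93.4% with 76 per arm after 10% dropout. The claim of at least 90% is reproduced. The plan gives no figure for interval coverage.

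**Intervals at low counts.** Wald at k = 1: p = 1/85 = 0.0118; √(0.0118 × 0.9882/85) = 0.0117; 1.96 × 0.0117 = 0.0229; limits −1.1% and 3.5%. The lower limit is negative whenever k < 3.84(1 − p), which at N = 85 means k = 1, 2 or 3. Wilson limits are [p + z²/2N ± z√(p(1−p)/N + z²/4N²)]/(1 + z²/N). At k = 0 the Wilson upper limit is 3.84/(85 + 3.84) = 4.3%.

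| Responders of 85 | Wald | Wilson | Clopper-Pearson |
|---|---|---|---|
| 0 | 0 to 0% | 0 to 4.3% | 0 to 4.2% |
| 1 | −1.1 to 3.5% | 0.2 to 6.4% | 0.0 to 6.4% |
| 2 | −0.9 to 5.6% | 0.7 to 8.2% | 0.3 to 8.2% |
| 3 | −0.4 to 7.5% | 1.2 to 9.9% | 0.7 to 10.0% |
| 4 | 0.2 to 9.2% | 1.9 to 11.5% | 1.3 to 11.6% |

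**Exact coverage.** For each assumed true rate, sum the binomial probabilities of every k from 0 to 85 whose interval contains that rate.

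| Assumed true rate | Wald | Wilson | Chance of k = 0 | Chance of k = 1 to 3 |
|---|---|---|---|---|
| 0.5% | 34.7% | 93.2% | 65.3% | 34.6% |
| 1% | 57.4% | 94.6% | 42.6% | 56.4% |
| 2% | 81.9% | 97.2% | 18.0% | 72.9% |
| 3% | 92.1% | 95.7% | 7.5% | 67.3% |
| 4% | 85.2% | 94.6% | 3.1% | 52.6% |
| 5% | 92.7% | 96.1% | 1.3% | 36.8% |
| 8% | 90.9% | 95.5% | 0.1% | 8.3% |
| 10% | 92.6% | 93.3% | 0.0% | 2.4% |
| 15% | 93.9% | 95.4% | 0.0% | 0.1% |
| 20% | 95.3% | 95.9% | 0.0% | 0.0% |

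The losses can be traced by hand. At 1%, the zero-width interval at k = 0 misses, which alone costs 42.6 points: 100 − 42.6 = 57.4. At 4%, both k = 0 (3.1%) and k = 1 (upper limit 3.5%; probability 0.0311 × 85 × 0.04/0.96 = 11.0%) miss, leaving 85.9%. The upper tail takes it to 85.2%. Coverage therefore does not rise smoothly between 3% and 5%.

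Clopper-Pearson coverage is at least 95.4% over the same range.

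**Where the formula works.** At the ASAS 40 planning rates Wald coverage is 95.3% (20%) and 95.0% (46%). For the treatment difference, the Wald interval covers 94.1% to 94.4% for active rates of 15% or 20% against placebo rates of 1%, 2% or 5% (five pairs), and 94.7% for 46% against 20%.

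**The case against.** The strongest reply is that the poor coverage depends on a rate the documents never state. No placebo figure is given for partial remission, ASDAS inactive disease or early ASAS 40. The only remission figure, 15% to 20%, describes available treatment. The 57% needs a true rate of 1%; at 5%, 8% and 10% coverage is 91% to 93%, and at 20% the problem is gone. This stands: the behaviour of the formula is certain, but whether this trial meets it is not known from the documents.

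Second, nothing inferential rests on these limits. A reader might infer that, because partial remission is in the multiplicity-controlled set, its significance claim is compromised. The documents do not support that. The Hochberg step in Section 9.2.5 takes its binary-endpoint p-values from the CMH test, and the estimand is the difference between arms. ASDAS inactive disease and early ASAS 40 carry nominal p-values only.

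Third, a reader might extend the point to the primary endpoint or to Period 2. Coverage at the ASAS 40 planning rates is nominal. After Week 14 everyone still on treatment receives upadacitinib, so the near-zero placebo argument does not carry over. Section 9.3 also adds model-based intervals.

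Fourth, SAP Section 11.0 records the Week 14 lock as completed in February 2019, and Section 4.4 describes that analysis as unblinded. Replacing a prespecified interval afterwards is not just a code edit. This stands and shapes the fix.

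A reader given k and N can compute better limits, but that does not justify printing 0% to 0% as a 95% interval.

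**Conclusion.** The point holds as a minor reporting defect. A fixed rule with no low-count provision gives zero-width or negative limits at zero to three responders out of 85. It covers about 57%, 82% and 85% at true rates of 1%, 2% and 4%. These coverage figures rest on the assumed rates and on 85 subjects per arm; the limits at each count rest on the SAP's formula and N alone.

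The scope is single-arm estimates at low rates: chiefly placebo ASAS partial remission, then ASDAS inactive disease and early-visit ASAS 40 in Period 1. The p-values and type I error do not use these intervals. The treatment-difference interval is close to nominal at the pairs checked, and the primary ASAS 40 result shows no defect at its planning rates.

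**What to change.** In Appendix C, specify Wilson limits (or Clopper-Pearson, if at-least-nominal coverage is preferred) for single-arm response rates, and align the wording in Sections 9.2.3 and 9.2.4, where it matters. The code change is a different limit type within the existing PROC FREQ BINOMIAL option, with the output step keeping those limits. The CMH test and the difference interval stay as they are.

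Using the same method in Sections 9.2.1 and 9.3 is for consistency only and corrects no demonstrated error.

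For Week 14, keep the prespecified Wald limits and report Wilson limits beside them, documented as a supplementary interval added after the lock. For the Week 104 and final locks, where binary rates are reported, use Wilson limits prospectively.

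The cost is slightly asymmetric intervals, a short SAP amendment and a documented post-lock addition. No new data or test is needed.
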